## 1 Background

Environmental hygiene is a key component of infection prevention in healthcare, and a driver of healthcare associated infections. Staff who clean in many low resource countries receive no formal training on cleaning, waste disposal and linen handling. This issue has been exacerbated by the COVID-19 pandemic. The only recommended training on environmental hygiene for low resourced facilities, TEACH CLEAN, uses a training of trainers model. A selected cadre of “champions” is trained which in turn train their peers with responsibilities on environmental hygiene at the facility level. Early pilot data to test its effectiveness of this training package are very promising.

We will evaluate the effectiveness of an environmental cleaning bundle to improve microbiological cleanliness in Cambodian hospitals.

## 2 Objectives

The main aims of the trial are to assess the extent of 1) improvement in microbiological cleanliness of near-patient surfaces (primary outcome), and 2) decrease/reduction in the level of contamination and presence of an important healthcare pathogen, *S. aureus*.

## 3 Study Methods

### 3.1 *Trial design*

This study is a multicentre stepped wedge cluster randomized trial conducted in thirteen public hospitals (the trial clusters) in Cambodia. This study has four distinct steps. In each of the steps, either 3 or 4 hospitals (picked at random) will receive the intervention.

The intervention is based on the training package published in March 2023 by the World Health Organisation (WHO) entitled “Environmental cleaning and infection prevention and control in healthcare facilities in low- and middle-income countries”. The intervention relies on a pre-publication version of this package and its predecessor, TEACH CLEAN, on which the WHO package is primarily based. The intervention consists of three main phases. Phase 1 consists of preparatory activities, and it involves all hospitals at the same time. Phase 2 is the training of the Cleaning Champions, the timing of which is established by randomization. Phase 3 is the ongoing mentorship of cleaning champions while they trained and supervised cleaning staff. We consider the trial intervention subject to randomization as the training of facility cleaning champion (phase 2) and their mentorship (phase 3).

	Clusters/HOSPITALS	2022										2023	
		MAY	JUNE	JULY	AUGUST	SEPTEMBER	OCTOBER	NOVEMBER	DECEMBER	FEBRUARY	MARCH		
		PERIOD 1		PERIOD 2		PERIOD 3		PERIOD 4		PERIOD 5			
Sequence 1 Clusters = 3; Cluster size = 30	1	0	0	1	1	1	1	1	1	1	1		
	2	0	0	1	1	1	1	1	1	1	1		
	3	0	0	1	1	1	1	1	1	1	1		
Sequence 2 Clusters = 3; Cluster size = 30	4	0	0	0	1	1	1	1	1	1	1		
	5	0	0	0	1	1	1	1	1	1	1		
	6	0	0	0	1	1	1	1	1	1	1		
Sequence 3 Clusters = 4; Cluster size = 30	7	0	0	0	0	0	1	1	1	1	1		
	8	0	0	0	0	0	1	1	1	1	1		
	9	0	0	0	0	0	1	1	1	1	1		
Sequence 4 Clusters = 3; Cluster size = 30	10	0	0	0	0	0	1	1	1	1	1		
	11	0	0	0	0	0	0	0	1	1	1		
	12	0	0	0	0	0	0	0	0	1	1		
	13	0	0	0	0	0	0	0	0	1	1		

**Figure 1.** Stepped wedge design with intervention (1) and control periods (0). The intervention period represents the time when the training occurred at the facility level.

### 3.2 Randomization

We used constrained randomization to ensure there was balance in two hospital characteristics in each randomization step: hospital level (i.e. Complimentary Package of Activities – CPA – which defines the type of clinical services offered: level 3 – the highest level- vs levels 1 or 2) and the region (i.e. within Battambang province vs other provinces). There were, in total, three CPA3 hospitals, one in each province, and seven hospitals situated in Battambang. We performed a public randomization – picking from “a hat” – in a virtual ceremony in February 2022, which involved all the key study coordinators (NIPH, WaterAid, DHS and LSHTM). Keeping the constrained rules described above, a representative from each coordinating organization had one of three hats (one for CPA3 hospitals; one for Battambang non-CPA3 hospitals; one for other provinces and non-CPA3 hospitals); each representative picked one cluster from their hat for each of the four designed steps. The procedures for randomization were agreed with an independent statistician.

### 3.3 Sample size

We calculated that with 30 surface samples in each hospital and with a pre-intervention cleanliness proportion ranging from 30% to 50%, we would have 85% power to detect a 30% relative increase in microbiological cleanliness. This is based on a two-sided 5 % significance level, a two-period decay correlation structure with conservative estimates of within-period intraclass correlation coefficient (ICC) in microbiological cleanliness at 0.03 (previous pilot), observation auto-correlation at 0.6 and cluster auto-correlation at 0.6. The pre-intervention cleanliness proportion and the within-hospital ICC were estimated using pilot data from similar-level maternity wards in Tanzania as no local data was available in Cambodia on microbiological cleanliness. For the power calculations, we used the website (<https://clusterrcts.shinyapps.io/rshinyapp/>) and underlying formula operationalized by Hemming et al. (2020) in March 2021.

### 3.4 Framework

All comparisons performed in this trial will be for superiority, with the hypothesis that the cleaning intervention will improve cleanliness compared to the control arm.

### ***3.5 Statistical interim analysis and stopping guidance***

There are no interim analyses planned and no stopping guidance.

### ***3.6 Timing of final analysis***

The final analysis will be performed after the last hospital site visit is conducted and the data have been cleaned. The plan is for the last visit to be undertaken in March 2023, with analysis in summer 2023.

### ***3.7 Timing of outcome assessment***

The primary outcome measure was a binary assessment of the cleanliness of hospital surfaces (binary clean versus not clean) performed using dipslides. We collected 30 double-sided dipslide samples from surfaces in three wards in each hospital every month: 12 from the maternity ward, 10 from the pediatric ward and 8 from a general medicine ward. Data collection was planned once a month for 10 months in each of the 13 hospitals. The time of the visit varied each month so that the hospital staff did not know when it would occur.

## **4 STATISTICAL PRINCIPLES**

### ***4.1 Confidence intervals and p-values***

We will present 95% confidence intervals and p-values. However, we will not claim significance based on a p-value cut off point. In line with current debates, we will focus on the effect of the intervention, plausible mechanisms via which intervention would work, data quality, study design, bias and the real-world impact, rather than p-values in isolation.

### ***4.2 Analysis population***

There are three analysis populations:

1. an individual sample level population, consisting of every surface sample taken during the study,
2. a hospital-level population, consisting of hospital-level summaries of the outcome variables (averages for continuous variables, proportions for binary variables)
3. a ward-level population, consisting of ward-level summaries of the outcome variables (averages for continuous variables, proportions for binary variables)

[figure not shown]
## **5 TRIAL POPULATION**

### ***5.1 Eligibility***

We approached all eligible hospitals [i.e. all public district or provincial referral hospitals] to maximise the feasibility of the trial; all participated. The hospitals are located across three selected provinces in Cambodia: Kampong Chhnang, Battambang and Kratie.

## 5.2 Information to be included in the CONSORT flow diagram

Reporting is based on the extension of the CONSORT guidelines for stepped wedge cluster randomised studies

**Figure 2** (Shell figure). Flow diagram

## 5.3 Withdrawal / Follow-up

In the event that a hospital withdraws from the study after randomization it will not be replaced, as we have already recruited all eligible hospitals.

## 5.4 Baseline patient characteristics

Baseline characteristics will be described by "randomisation step" and the following statistics will be reported: mean, standard deviation, median, IQR, for the following characteristics: cleanliness, temperature, patient volume and number of beds per cleaner.

**Table 1** (Shell table). Baseline characteristics (month 1 and 2) of the surface samples.

Sequence:	S1	S2	S3	S4
Dipslides analyzed	% or mean (SD)			
Estimate	3	3	4	3
Number of hospitals				

Primary binary outcome				
Cleanliness				
Pre-specified confounders				
Temperature (degrees)				
Patient volume (number of patients)				
Number of beds per cleaner				

## 6 ANALYSIS

### 6.1 *Outcome definitions*

#### 6.1.1 *Primary outcome*

A surface will be rated as “clean” if it has an Aerobic Colony Count (ACC) less than 2.5 colony forming units (CFU)/cm^2.

#### 6.1.2 *Secondary outcomes*

There are two secondary outcomes:

- the estimated number of CFU per slide
- presence or absence of *S. aureus* from the selective media on the other side of the dipslide

For the estimated number of CFU per slide we will use the categorical scoring of contamination (as shown below) and use the used the category mid-point in analyses as a continuous outcome. We reversed the order so higher number indicate greater cleanliness (100 – midscore). For example

Original category range	Contamination score used in analysis
0	100
>0 to <2.5	98.75
2.5-12	95.25
12-40	74
>40-	30

100	0
-----	---

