## 6.2 Analysis methods

For the primary outcome (binary: clean vs not clean) we will use a generalised estimating equation (Stata **xtgee** command) with exchangeable equation structure using sample level data (i.e. surface sampled), accounting for within hospital clustering, with small sample Kauermann-Carroll correction. We will use a binomial distribution and logit link to estimate an odds ratio. Each cluster, hospital, will be analysed according to the actual time when training occurred independently of when training was planned

For all analyses we will adjust for the design factors: stratification variables which are CPA – hospital level - and province, both binary; and calendar time included as a categorical variable in the model). We will also adjust for four a priori potential confounders:

- number of beds per cleaner at the hospital level (linear),
- number of patients on the ward (linear) – time-dependent (monthly measurements)
- temperature of the ward (linear) – time-dependent (monthly measurements)
- surface type (3 categorical levels)

We will use a similar strategy for secondary outcomes. For 2.1 we will use generalized estimating equations again using **xtgee** with a normal distribution and the identity link function.

We will in addition also conduct similar analyses on ward- and hospital-level averages for all outcomes. In these analyses, we will include a single variable which indicated the proportion of samples taken from bed rails (the largest category).

The main results will be presented in a table as follows:

**Table 2** (Shell table). Unadjusted and adjusted primary and secondary outcome results estimating the effect of the intervention on microbiological cleanliness a) clean vs unclean; b) contamination score.

	Unadjusted*	CI	Adjusted**	CI	p-value
Primary (pre-specified) outcome					
Individual samples dataset					
a) Binary clean vs no clean (Unit: odds ratio)					
Exploratory (pre-specified) outcomes					
Individual samples dataset					

b) Contamination score (Unit: number of CFU per displide)					
Hospital/Ward summaries dataset					
a) Binary clean vs no clean (Unit: avg %)					
b) Contamination score (Unit: average CFU per dipslide)					

\*Accounts for clustering, time, and stratification variables

\*\* Accounts for clustering, time, and stratification variables. Adjusted for temperature, patient volume, number of beds per cleaner and surface type.

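### The SAP's scoring rule gives 92.75 for the 2.5-12 contamination category, but its score table lists 95.25

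*SAP*

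**What the plan says.** SAP section 6.1.2 names two secondary outcomes. The first is "the estimated number of CFU per slide". It is derived from categories of contamination: the analysis will "use the used the category mid-point in analyses as a continuous outcome". The scale is then turned round by taking 100 minus the mid-point: "We reversed the order so higher number indicate greater cleanliness". A table follows, introduced as an example, with a column headed "Contamination score used in analysis". It gives 95.25 for the 2.5-12 category.

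SAP section 6.2 models this score by GEE "with a normal distribution and the identity link function", and plans similar analyses on ward-level and hospital-level averages. In the Table 2 shell the score sits under "Exploratory (pre-specified) outcomes", and its two rows are labelled "Contamination score (Unit: number of CFU per displide" and "Contamination score (Unit: average CFU per dipslide" (each label closes with a bracket).

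**The concern.** The rule and the table cannot both be followed for the 2.5-12 category. The column heading presents the tabulated values as the ones to be analysed, so an analyst could reasonably code 95.25.

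The score is treated as continuous with an identity link, so a category value that is off by a fixed amount passes straight into the estimated mean difference. This band lies immediately above the >0 to <2.5 category. With 95.25, a slide that improves from 2.5-12 to >0 to <2.5 is credited with too little, and a slide that improves from 12-40 to 2.5-12 is credited with too much. Moves that skip the band carry no error.

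A separate point concerns labelling. Table 2 gives a CFU count as the unit of a score on which higher means cleaner, so a positive effect could be read as more contamination. The unit of the category bands is also unclear: the outcome is named per slide, but the 2.5 boundary equals the primary outcome's cut-off in section 6.1.1, which is per cm².

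**Working it through.** **Inputs.** The category bounds, the stated scores and the rule all come from SAP section 6.1.2. The 30% and 39% clean used in step 4 come from the Figure 2 parameters in protocol section 3.4.2.

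**1. Apply the rule to every row.** Score = 100 − (lower + upper)/2.

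| Category | Mid-point | Score by rule | Score in table |
|---|---|---|---|
| 0 | 0 | 100 | 100 |
| >0 to <2.5 | 1.25 | 98.75 | 98.75 |
| 2.5-12 | 7.25 | **92.75** | **95.25** |
| 12-40 | 26 | 74 | 74 |
| >40-100 | 70 | 30 | 30 |
| 100 | 100 | 0 | 0 |

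The last two rows are split in the text available for review; they are read here as >40-100 and 100. Only the 2.5-12 row fails, by 95.25 − 92.75 = 2.5.

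**2. Look for another rule that gives 95.25.**

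- Half-width: 100 − (12 − 2.5)/2 = 100 − 4.75 = 95.25. The same formula gives 86 for 12-40 and 70 for >40-100, against 74 and 30 in the table. A half-width slip in this one row is a likely cause, but that is inference.
- Geometric mid-point: 100 − √(2.5 × 12) = 94.52.
- Other bounds: 3-12 gives 92.5, 2-12 gives 93.0 and 2.5-11 gives 93.25. A range of 2.5-7 gives 95.25 but leaves 7 to 12 unscored, because the next category starts at 12.

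No single alternative rule reproduces the table.

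**3. Effect on the gain for one slide.**

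| Move | By rule | As tabulated | Relative error |
|---|---|---|---|
| 2.5-12 to >0 to <2.5 | 6.0 | 3.5 | −41.7% |
| 2.5-12 to 0 | 7.25 | 4.75 | −34.5% |
| 12-40 to 2.5-12 | 18.75 | 21.25 | +13.3% |
| >40-100 to 2.5-12 | 62.75 | 65.25 | +4.0% |
| 100 to 2.5-12 | 92.75 | 95.25 | +2.7% |
| 12-40 to >0 to <2.5 | 24.75 | 24.75 | 0% |

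**4. Effect on a mean difference.** Error = 2.5 × Δp, where Δp is the difference between conditions in the proportion of slides in the 2.5-12 band. The documents do not give Δp. For Δp of 0.05, 0.10 and 0.20 the error is 0.125, 0.25 and 0.50 points.

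As an illustration, take the protocol's rise in clean surfaces, 0.39 − 0.30 = 0.09. Assume that all newly clean slides land in >0 to <2.5 and that nothing else moves.

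- All from 2.5-12: 0.09 × 6.0 = 0.54 by rule; 0.09 × 3.5 = 0.315 as tabulated (−42%).
- Half from 2.5-12, half from 12-40: 0.09 × 15.375 = 1.38 by rule; 0.09 × 14.125 = 1.27 as tabulated (−8%).
- All from 12-40: 0.09 × 24.75 = 2.23 either way (0%).

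**The case against.** The strongest reply is that the harm is conditional and small. The rule is stated in prose and the table is introduced as an example, so an analyst who codes from the rule gets 92.75 and no result changes. The score is one of two secondary outcomes, and Table 2 calls it exploratory. SAP section 4.1 says significance will not be claimed from a p-value cut-off. Even with Δp at 0.20, the error is 0.5 points on a 0-100 scale, and if all movement is towards cleaner it cannot reverse the sign. The percentage errors do not depend on the 0.09, which cancels; it comes from the primary outcome's power calculation, and the documents set no target for the score.

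Most of this stands. The documents do not show which value was or will be coded, so any effect on results is conditional. The −42% and +13% are limits, and the absolute formula in step 4 is the better summary. The reading of the last two table rows is a reconstruction, but the intact rows (100, 98.75 and 74) are enough to establish the rule.

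The objection does not remove the contradiction. An example of a rule should obey it, and the column heading says these are the values analysed. The 2.5-12 row is intact in the text, and nothing elsewhere gives a different score for this band.

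**Conclusion.** The concern holds. The SAP's own rule gives 92.75 for the 2.5-12 category and its table says 95.25. The rule and the remaining rows agree on which value is out of line.

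If 95.25 is coded, the error in a mean difference is 2.5 × Δp, at most 0.5 points on the assumption that Δp lies within ±0.20. The relative error lies between −42% and +13% if all movement is towards cleaner. If 92.75 is coded, only the table is wrong.

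The reach is limited to the contamination score and its ward-level and hospital-level averages. The primary outcome uses only the 2.5 CFU/cm² cut-off, and neither it nor the *S. aureus* outcome nor the sample size is touched. This should be fixed because a pre-specified outcome value is wrong as written and the correction is nearly free; it does not threaten the trial's main conclusion.

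**What to change.** 1. Check which value the recode uses for the 2.5-12 category.
2. Replace 95.25 with 92.75 in the section 6.1.2 table, as a dated and documented correction.
3. If 95.25 was already used, rerun the contamination-score models at sample, ward and hospital level.
4. In both Table 2 rows, label the outcome as a reversed score (100 minus category mid-point, higher = cleaner) in place of a CFU count.
5. State whether the category bands are CFU per slide or CFU/cm².

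The cost is one table value, a check of the recode, two labels and one clarifying statement. Sections 3.7 and 6.1.2 use the past tense in places, while section 3.6 still describes the last visit as planned for March 2023, so the documents do not settle whether data existed when the table was written. The correction should therefore carry its date. If results already exist, reporting the score under both values would show that the change was not made because of them.

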## 6.2 Analysis methods

For the primary outcome (binary: clean vs not clean) we will use a generalised estimating equation (Stata **xtgee** command) with exchangeable equation structure using sample level data (i.e. surface sampled), accounting for within hospital clustering, with small sample Kauermann-Carroll correction. We will use a binomial distribution and logit link to estimate an odds ratio. Each cluster, hospital, will be analysed according to the actual time when training occurred independently of when training was planned

For all analyses we will adjust for the design factors: stratification variables which are CPA – hospital level - and province, both binary; and calendar time included as a categorical variable in the model). We will also adjust for four a priori potential confounders:

- number of beds per cleaner at the hospital level (linear),
- number of patients on the ward (linear) – time-dependent (monthly measurements)
- temperature of the ward (linear) – time-dependent (monthly measurements)
- surface type (3 categorical levels)

We will use a similar strategy for secondary outcomes. For 2.1 we will use generalized estimating equations again using **xtgee** with a normal distribution and the identity link function.

We will in addition also conduct similar analyses on ward- and hospital-level averages for all outcomes. In these analyses, we will include a single variable which indicated the proportion of samples taken from bed rails (the largest category).

The main results will be presented in a table as follows:

**Table 2** (Shell table). Unadjusted and adjusted primary and secondary outcome results estimating the effect of the intervention on microbiological cleanliness a) clean vs unclean; b) contamination score.

	Unadjusted*	CI	Adjusted**	CI	p-value
Primary (pre-specified) outcome					
Individual samples dataset					
a) Binary clean vs no clean (Unit: odds ratio)					
Exploratory (pre-specified) outcomes					
Individual samples dataset					

b) Contamination score (Unit: number of CFU per displide)					
Hospital/Ward summaries dataset					
a) Binary clean vs no clean (Unit: avg %)					
b) Contamination score (Unit: average CFU per dipslide)					

\*Accounts for clustering, time, and stratification variables

\*\* Accounts for clustering, time, and stratification variables. Adjusted for temperature, patient volume, number of beds per cleaner and surface type.

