### 6.4 Additional analyses

We will estimate the absolute risk *difference* of binary outcomes, using generalized estimating equations with an identity link function, and a standard binomial distribution.

We will calculate the ICC for the primary outcome.

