- The key independent variable will be the intervention (yes/no). The intervention variable will switch from “no” to “yes” after the first full month of the training
- Characteristics of the individual sites and clusters will be summarised by exposure status so to allow consideration of selection biases and lack of balance.
- These characteristics can be compared by randomisation step. This will include the numbers analysed, the average cluster size, and cluster characteristics
- A few characteristics of the hospital (e.g. size) will be considered as independent variables as these should remain roughly constant throughout the study.
- Each cluster will be analysed according to the actual time when it was “trained” independently on when this was planned for.
- Calendar time is associated with both the exposure to the intervention and also possibly the outcome, and so is a potential confounder and will be adjusted for in the analysis
- Adjusting for the systematically different observation periods and for clustering in the data will be accomplished.
- We will test the residuals of the model to look for autocorrelation over time and will check for influential observations.
- The estimated intra-cluster correlation and time effect from the fitted model will be reported both for use in the design of future trials and to allow appreciation of any underlying confounding effects of calendar time
- We will consider using a small sample correction.

In addition, using the same general model we will create a variable indicating the strength of implementation which we will use as an alternative exposure variable to the simpler *intervention vs control variable*. We will also explore descriptively time trends for each cluster. Finally, we will analyse the knowledge and attitudes descriptively (and by implementation *strength and by microbiological outcomes*) as these measures are only collected at the end of the trial.

Qualitative data from FGDs and observations will be analysed adopting a generalised qualitative approach in which the transcripts were disassembled into low-level descriptive codes and then reassembled into themes that may help explain the observed outcomes

4 Data and reporting

Please refer to our exhaustive data management plan as in Appendix 7. The Consort 2018 extension to stepped wedge randomised trials will be used (16).

5 Ethical approval and consent

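### Exposure follows actual training time and no outcome estimate by randomised step is planned; one sensitivity analysis would keep the randomised comparison in view if timings slip (minor)

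*SAP*

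**What the plan says.** SAP 6.2 fixes the coding for the primary model: "Each cluster, hospital, will be analysed according to the actual time when training occurred independently of when training was planned". The protocol's data analysis list (3.4.2) agrees: "Each cluster will be analysed according to the actual time when it was" trained, whatever the plan was.

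What is randomised is the matching of hospitals to the four training periods (protocol 3.1). SAP 3.1 names champion training and the mentorship that follows as the randomised intervention.

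The randomised step appears only in descriptive work. SAP 5.4: "Baseline characteristics will be described by" randomisation step. Protocol 3.4.2: "These characteristics can be compared by randomisation step".

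The other planned outcome analyses do not use it:
- SAP 4.2 and 6.2 list sample-, ward- and hospital-level models.
- SAP 6.4 adds a risk difference and one more item: "We will calculate the ICC for the primary outcome".
- The protocol adds descriptive time trends per hospital and "a variable indicating the strength of implementation which we will use as an alternative exposure variable", which is not randomised.

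On the lag, the protocol switches exposure on "after the first full month of the training" and assumes a one-month delay for sample size. SAP 6.2 states no lag, and the caption to SAP Figure 1 dates the intervention period from facility-level training.

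**The concern.** Actual dates arise after randomisation. Protocol section 6 accepts that intended timings may fail, for example in lockdowns, and protocol 3.3.2 has training timed with hospital and ward managers. If the hospitals that run late are less clean at the time, coding by actual date moves their poor months from the exposed to the unexposed side and biases the estimate upward. If cleaner hospitals run late, it is biased downward. Adjustment for month, hospital level, province and the four listed covariates does not remove cleanliness differences that those variables miss.

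At stake is whether readers will have, beside the primary result, an estimate that rests on the random allocation alone.

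**Working it through.** **1. Reproducing the plan's power.** Inputs from SAP 3.3 and 3.7 and protocol 3.4.2: 13 hospitals (3, 3, 4, 3 per step), 10 months, 30 surfaces, 0.30 against 0.39, within-period ICC 0.03, cluster and observation auto-correlation both 0.6, two-sided 5%. Power = Φ(effect/SE − 1.96), with the SE from generalised least squares on hospital-month means with categorical month, cluster correlation decaying by month and observation correlation constant. With 8, 7, 5 and 2 exposed months per step, power is 84.2%; with 8, 6, 4 and 2 it is 84.8%. The SAP states 85%, so the set-up reproduces the design. The 84.2% implies SE = 9/(1.96 + 1.00) ≈ 3.04 points.

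**2. Assumptions about delay.** The documents give no number, length or cause of delays, so these are illustrative. No true effect; half of the hospitals one month late, which recodes 6.5 of 13 × 10 = 130 hospital-months; first exposed months 3, 5, 7 and 9; champion training one month earlier. Strong dependence: the less clean hospitals are the late ones. Weak: 70% against 30% chance of delay. The model has month dummies, the SAP's exchangeable structure and no covariates. There were 20,000 trials per scenario, with observation correlation run both as decaying and as constant.

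**3. Bias of the actual-time estimate under the null.**

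| Delay depends on cleanliness in | Weak to strong (points) | Odds ratio, strong (truth 1) |
|---|---|---|
| month before champion training | +0.1 to +0.3 | 1.01–1.02 |
| the 10-month average | +0.2 to +0.4 | 1.02–1.03 |
| champion-training month | +0.4 to +1.1 | 1.05–1.06 |
| first planned exposed month | +1.0 to +2.5 | 1.13 |
| nothing (unrelated) | 0.0 | – |

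The design effect is 39 − 30 = 9 points, or an odds ratio of (0.39/0.61)/(0.30/0.70) = 1.49. Coding by randomised step gave bias within simulation error of zero. Reversing the dependence gives about the same size with a minus sign. If whole steps slip together, strong dependence gives +0.1 (month before) or +0.5 (champion month).

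**4. Type I error.** For bias b and standard deviation s, it is 1 − Φ(1.96 − b/s) + Φ(−1.96 − b/s). With s = 3.43, b = 1.1 gives about 6% and b = 2.5 about 11%.

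**5. Sensitivity.**
- With the correct covariance instead of the exchangeable one, the strong champion-month bias falls from 1.09 to 0.03 (decaying) or from 1.05 to 0.40 (constant). Part of it therefore comes from the working structure.
- Harsher assumptions raise the figures. With the 3 to 6 least clean hospitals late by one to two months, bias is +0.6 to +1.3 if persistent cleanliness drives delay. It is +1.8 to +3.3 if cleanliness in the first planned exposed month does.

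**6. What the added estimate would look like.** With a true 9.0 points and one-month delays unrelated to cleanliness in 10%, 25% or 50% of hospitals, the randomised-step estimate averages 8.6, 8.0 or about 7. Power falls from 82% to 78%, 71% or 59% under the exchangeable structure, and from 87% to 82%, 72% or 54% with the correct covariance. At 50% late, dilution alone makes a mean gap of 9.0 − 6.9 = 2.1 points. With no effect and unrelated delay, the gap still has a standard deviation of 1.9 to 2.1 points.

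**The case against.** The rule is deliberate and the same in both documents, so there is no ambiguity between planned and actual time, and it is a legitimate choice. The one cause of slippage that is named, lockdowns, is external to surface cleanliness, and managers are consulted for staff availability. Champion training is given to three or four hospitals within the same four weeks, so whole-step slippage is the natural case, and there the bias is at most about 0.5 points. In most scenarios the bias is at most about a third of one standard deviation of the estimate (1.1/3.1 ≈ 0.35). The simulations omit the SAP's covariates. A diluted companion estimate could also cast doubt on a real effect.

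All of this stands, and it is why the point is minor. It does not supply the missing estimate: hospital time trends are descriptive, and training records alone give no effect by randomised step.

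Three stronger readings are tempting, and the documents do not support them:
- That the primary estimate is biased. Nothing shows that delays happened or relate to cleanliness, and irregular rows in the extracted Figure 1 tables are not evidence of delay.
- That comparing the two estimates would reveal bias. Dilution and chance both produce gaps as large as the bias in question.
- That the two analyses must agree if training keeps to schedule. They coincide only if champion training is on time and facility training follows at exactly the assumed lag.

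**Conclusion.** The gap is real, and filling it is a cheap improvement of minor severity. The plan contains no outcome estimate that rests on the randomised step. The consequence is conditional: zero if delay is unrelated to cleanliness; about 0.1 to 1.1 points under the assumed one-month delays in half the hospitals and the exchangeable structure; about 2.5 points only under strong dependence on the first planned exposed month; and more only if delays are longer. These sizes rest on assumed delay mechanisms and on the plan's own ICC and auto-correlations. The textual finding does not depend on them. The actual-time analysis can remain primary.

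**What to change.** Keep the actual-time analysis as primary, and:

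1. State in SAP 6.2 which event, champion or facility training, and which lag define exposure, so that the two codings differ only through departures from plan.
2. Add to SAP 6.4 a sensitivity analysis of the primary outcome: the same model, with exposure set by each hospital's randomised step on one named planned calendar, fixed before analysis, and the same stated lag for every hospital in a step. The Figure 1 calendars must be reconciled first: the SAP's months skip January and end in March, while the protocol's include January and end in February.
3. Report planned and actual champion and facility training dates for each hospital.
4. Say in advance that a gap between the estimates may reflect dilution or chance and is not a test for bias.

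The cost is one recoded variable, one model run and one table, drawing on training records already to be collected (protocol 3.4.1). The primary analysis keeps its power. The price is that, if delays occur, the added estimate is diluted and less powerful.
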